4.4. Salvage Therapy

Patients who progress or who cannot tolerate therapy should be considered for other therapy as appropriate.

5. Safety reporting

All subjects who receive at least one dose of study drug will be evaluable for safety. Investigators and all appropriate staff should review and have access to the Common Terminology Criteria for Adverse Events (CTCAE) v4.0, published May 28, 2009 by the US National Cancer Institute (NCI), which can be downloaded from the NCI website http://ctep.cancer.gov/reporting/ctc.html. The reported AE term and CTC severity grade should correspond to the term and severity grade included in the relevant source document/clinic chart. The investigator must endeavor to obtain sufficient information to determine the causality of the adverse event (i.e., study drug, other illness, progressive malignancy, etc.) and must provide his/her opinion of the causal relationship between each AE and each study drug.

5.1. Adverse Events

All observed or volunteered adverse events regardless of suspected causal relationship to the investigational product(s) will be recorded on the adverse event page(s) of the case report form (CRF).

For all adverse events, the investigator must pursue and obtain information adequate both to determine the outcome of the adverse event and to assess whether it meets the criteria for classification as a serious adverse event requiring immediate notification to Pfizer or its

designated representative (see Section 5.4). For all adverse events, sufficient information should be obtained by the investigator to determine the causality of the adverse event. The investigator is required to assess causality and indicate that assessment on the CRF. Follow-up of the adverse event, after the date of therapy discontinuation, is required if the adverse event or its sequelae persist. Follow-up is required until the event or its sequelae resolve or stabilize at a level acceptable to the investigator and the Pfizer medical monitor.

5.2. Definition of an Adverse Event

An adverse event is any untoward medical occurrence in a clinical investigation subject administered a product or medical device; the event need not necessarily have a causal relationship with the treatment or usage. Examples of adverse events include but are not limited to:

- Abnormal test findings;
- Clinically significant symptoms and signs;
- Changes in physical examination findings;
- Hypersensitivity;
- Progression/worsening of underlying disease;
- Lack of effect.

Additionally, they may include the signs or symptoms resulting from:

- Drug overdose;
- Drug withdrawal;
- Drug abuse;
- Drug misuse;
- Drug interactions;
- Drug dependency;
- Exposure in utero.

Lack of or insufficient clinical response, benefit, efficacy, or therapeutic effect should not be recorded as an adverse event. Progression of the malignancy under study should not be reported as an adverse event. However, if the malignancy has a fatal outcome during the trial or within the safety reporting period, then disease progression must be recorded as an adverse event (and an SAE with CTC grade 5 (see Section 5.6, Severity Assessment).

5.3. Abnormal Laboratory Findings

The criteria for determining whether an abnormal objective test finding should be reported as an adverse event are as follows:

Page 29 of 53

Protocol: 03/21/16

- Test result is associated with accompanying symptoms, and/or
- Test result requires additional diagnostic testing or medical/surgical intervention, and/or
- Test result leads to a change in trial dosing or discontinuation from the study, significant additional concomitant drug treatment, or other therapy, and/or
- Test result is considered to be an adverse event by the investigator or sponsor.

Merely repeating an abnormal test, in the absence of any of the above conditions, does not constitute an adverse event. Any abnormal test result that is determined to be an error does not require reporting as an adverse event.

5.4. Serious Adverse Events

A serious adverse event or serious adverse drug reaction is any untoward medical occurrence at any dose that:

- Results in death;
- Is life-threatening;
- Requires inpatient hospitalization or prolongation of existing hospitalization;
- Results in persistent or significant disability/incapacity;
- Results in congenital anomaly/birth defect.

Medical and scientific judgment should be exercised in determining whether an event is an important medical event. An important medical event may not be immediately life-threatening and/or result in death or hospitalization. However, if it is determined that the event may jeopardize the subject and may require intervention to prevent one of the other outcomes listed in the definition above, the important medical event should be reported as serious.

Examples of such events are intensive treatment in an emergency room or at home for allergic bronchospasm; blood dyscrasias or convulsions that do not result in hospitalization; or development of drug dependency or drug abuse.

5.5. Hospitalization

Adverse events reported from clinical trials associated with hospitalization or prolongation of hospitalization are considered serious. Any initial admission (even if less than 24 hours) to a healthcare facility meets this criteria. Admission also includes transfer within the hospital to an acute/intensive care unit (eg, from the psychiatric wing to a medical floor, medical floor to a coronary care unit, neurological floor to a tuberculosis unit).

Hospitalization does not include the following:

- Rehabilitation facilities;
- Hospice facilities;

- Respite care (eg, caregiver relief);
- Skilled nursing facilities;
- Nursing homes;
- Routine emergency room admissions;
- Same day surgeries (as outpatient/same day/ambulatory procedures).

Hospitalization or prolongation of hospitalization in the absence of a precipitating, clinical adverse event is not in itself a Serious Adverse Event. Examples include:

- Admission for treatment of a preexisting condition not associated with the development of a new adverse event or with a worsening of the preexisting condition (eg, for work-up of persistent pre-treatment lab abnormality);
- Social admission (eg, subject has no place to sleep);
- Administrative admission (eg, for yearly physical exam);
- Protocol-specified admission during a clinical trial (eg, for a procedure required by the trial protocol);
- Optional admission not associated with a precipitating clinical adverse event (eg, for elective cosmetic surgery);
- Pre-planned treatments or surgical procedures should be noted in the baseline documentation for the entire protocol and/or for the individual subject;
- Admission exclusively for the administration of blood products.

Diagnostic and therapeutic non-invasive and invasive procedures, such as surgery, should not be reported as adverse events. However, the medical condition for which the procedure was performed should be reported if it meets the definition of an adverse event. For example, an acute appendicitis that begins during the adverse event reporting period should be reported as the adverse event, and the resulting appendectomy should be recorded as treatment of the adverse event.

5.6. Severity Assessment

As required on the adverse event case report forms, the investigator will use the following definitions of Severity in accordance with Cancer Therapy Evaluation Program, Common Terminology Criteria for Adverse Events (Version 3.0, December 12, 2003) to describe the maximum intensity of the adverse event. If the event is serious, the CTC grade reported in the adverse event CRF must be consistent with the description of CTC grade included in the narrative section of the serious adverse event report.

GRADE	Clinical Description of Severity
0	No Change from Normal or Reference Range (This grade is not included in the Version 3.0 document but may be used in certain circumstances.)
1	MILD AE
2	MODERATE AE
3	SEVERE AE
4	LIFE-THREATENING OR DISABLING AE
5	DEATH RELATED TO AE

Note the distinction between the severity and the seriousness of an adverse event. A severe event is not necessarily a serious event. For example, a headache may be severe (interferes significantly with subject's usual function) but would not be classified as serious unless it met one of the criteria for serious adverse events, listed above.

5.7. Exposure In Utero

An exposure in-utero (EIU) occurs if a female becomes, or is found to be, pregnant either while receiving or having been exposed to (eg. environmental) an investigational medication or product, or the female becomes, or is found to be, pregnant after discontinuing and/or being exposed to the investigational medication or product.

If any trial subject becomes or is found to be pregnant while receiving an investigational medication/product, the investigator must submit this information to Pfizer medical monitor on an Exposure in Utero Form. This must be done irrespective of whether an adverse event has occurred and within 24 hours of awareness of the pregnancy. The information submitted should include the anticipated date of delivery (see below for information related to induced termination of pregnancy).

The investigator will follow the subject until completion of the pregnancy or until pregnancy termination (ie, induced abortion) and then notify Pfizer medical monitor of the outcome. The investigator will provide this information as a follow up to the initial Exposure in Utero Form. The reason(s) for an induced abortion should be specified. An EIU report is not created when an ectopic pregnancy report is received since this pregnancy is not usually viable. Rather, an SAE case is created with the event of ectopic pregnancy.

If the outcome of the pregnancy meets the criteria for immediate classification as a serious adverse event (ie, spontaneous abortion, stillbirth, neonatal death, or congenital anomaly [including that in an aborted fetus, stillbirth or neonatal death]), the investigator should follow the procedures for reporting serious adverse events.

Protocol: 03/21/16

In the case of a live birth, the "normality" of the newborn can be assessed at the time of birth (ie, no minimum follow-up period of a presumably normal infant is required before an Exposure in Utero Form can be completed). The "normality" of an aborted fetus can be assessed by gross visual inspection, unless pre-abortion test findings are suggestive of a congenital anomaly.

Page 32 of 53

Additional information about pregnancy outcomes that are classified as serious adverse events follows:

- "Spontaneous abortion" includes miscarriage and missed abortion.
- All neonatal deaths that occur within 1 month of birth should be reported, without regard to causality, as serious adverse events. In addition, any infant death after 1 month that the investigator assesses as possibly related to the in utero exposure to the investigational medication should be reported.

Discontinuations (See also Subject Withdrawal, Section 3.3) *5.8.*

The reason for a subject discontinuing from the trial will be recorded in the CRF. A discontinuation occurs when an enrolled subject ceases participation in the study, regardless of the circumstances, prior to completion of the protocol. The investigator must determine the primary reason for discontinuation. Withdrawal due to adverse event should be distinguished from withdrawal due to insufficient response, according to the definition of adverse event noted earlier, and recorded on the appropriate adverse event CRF page.

When a discontinuation is due to a serious adverse event, the serious adverse event must be reported in accordance with the reporting requirements defined below.

5.9. Eliciting Adverse Event Information

The investigator is to report all directly observed adverse events and all adverse events spontaneously reported by the trial subject. In addition, each trial subject will be questioned about adverse events at each clinic visit following initiation of treatment. The question asked will be "Since your last clinic visit you began taking the investigational medication have you had any health problems?"

5.10. Reporting Requirements (Serious and Nonserious)

Each adverse event is to be classified by the investigator as serious or nonserious. This classification determines the reporting procedures to be followed. If a serious adverse event occurs, expedited reporting will follow local and international regulations, as appropriate.

SAEs are reportable from the time that the subject provides informed consent, which is obtained prior to the subject's participation in the clinical trial, ie, prior to undergoing any trial-related procedure and/or receiving investigational product, through and including 28 calendar days after the last administration of the investigational product. Any serious adverse event occurring at any

Protocol: 03/21/16

other time after completion of the study must be promptly reported if a causal relationship to study drug is suspected.

Page 33 of 53

If a serious adverse event occurs, the Pfizer centralized SAE reporting system (see Appendix A) is to be notified within 24 hours of awareness of the event by the investigator. In particular, if the serious adverse event is fatal or life-threatening, notification to the Pfizer centralized SAE reporting system must be made immediately, irrespective of the extent of available adverse event information. This timeframe also applies to additional new information (follow-up) on previously forwarded serious adverse event reports.

In the rare event that the investigator does not become aware of the occurrence of a serious adverse event immediately (eg., if an outpatient trial subject initially seeks treatment elsewhere), the investigator is to report the event within 24 hours after learning of it and document the time of his/her first awareness of the adverse event.

For all serious adverse events, the investigator is obligated to pursue and provide information to the Pfizer centralized SAE reporting system in accordance with the timeframes for reporting specified above. In addition, an investigator may be requested by the Pfizer centralized SAE reporting system to obtain specific additional follow-up information in an expedited fashion. This information may be more detailed than that captured on the adverse event case report form. In general, this will include a description of the adverse event in sufficient detail to allow for a complete medical assessment of the case and independent determination of possible causality. Information on other possible causes of the event, such as concomitant medications and illnesses must be provided. In the case of a subject death, a summary of available autopsy findings must be submitted as soon as possible to Pfizer or its designated representative.

The investigator's assessment of causality must be provided. An investigator's causality assessment is the determination of whether there exists a reasonable possibility that the investigational product caused or contributed to an adverse event. If the investigator's final determination of causality is unknown and the investigator does not know whether or not study drug caused the event, then the event will be handled as "related to study drug" for reporting purposes. If the investigator's causality assessment is "unknown but not related to study drug", this should be clearly documented on study records. In addition, if the investigator determines the adverse event is associated with trial procedures, the investigator must record this causal relationship in the source documents and CRF, as appropriate, and report such an assessment in accordance with the serious adverse event reporting requirements, if applicable.

All adverse events will be reported on the adverse event page(s) of the CRF. It should be noted that the form for collection of serious adverse event information is not the same as the adverse event CRF. Where the same data are collected, the forms must be completed in a consistent manner. For example, the same adverse event term should be used on both forms. Adverse events should be reported using concise medical terminology on the CRFs as well as on the form for collection of serious adverse event information.

Nonserious adverse events are to be reported on the adverse event CRFs, which are to be submitted to Pfizer as specified in the adverse event report submission procedure for this protocol.

If a subject begins a new anticancer therapy, the adverse event reporting period will end at the time the new treatment is started. Death must be reported if it occurs during the serious adverse event reporting period after the last dose of investigational product, irrespective of any intervening treatment.

5.11. Abnormal Physical Examination Findings

Clinically significant changes, in the judgment of the investigator, in physical examination findings (abnormalities) will be recorded as adverse events.

6. DATA ANALYSIS/STATISTICAL METHODS

Detailed methodology for summary and statistical analyses of the data collected in this trial will be documented in an Analysis Plan, which will be dated and maintained by the sponsor. This documentation may modify the plans outlined in the protocol; however, any major modifications of the primary endpoint definition and/or its analysis will also be reflected in a protocol amendment.

6.1. Statistical Power and Sample Size Considerations

6.1.1. Sample Size

The primary purpose of this study is to determine the response rate in patients with advanced melanoma. This information would then be used to recommend further study of AG-013736 in this indication if favorable results occur. Implicit in this objective is the need to minimize the number of patients exposed to AG-013736 when unfavorable results occur.

These objectives are met through the use of a 2-stage Minimax design for Phase 2 protocols as discussed by Simon. The 2-stage design is used for testing hypotheses about the true response rate P. For each indication, we define p_0 , a response rate at which or below we consider AG-013736 to be ineffective or clinically unimportant, and p_1 , a minimum response rate that would merit further clinical development. The null hypothesis, H_0 , is $P \le p_0$. The alternate hypothesis, H_1 , is $P \ge p_1$.

The indication being studied in this protocol responds poorly to conventional chemotherapy. Therefore, p_0 and p_1 are set at low response rates of 5% and 20%, respectively. The α and β error rates are set at 0.10 and 0.10, respectively. These criteria result in a sample size for each stage of 18 and 14 patients (based on PASS 2002 software).

If enrolment to this study is stopped and AG-013736 is rejected at any stage because of lack of efficacy, the probability of falsely rejecting it is <0.10 when the true response rate is $\ge 20\%$. At the end of Stage 2, if AG-013736 is recommended for further study, the probability of failing to reject the agent is <0.10 when the true response rate is $\le 5\%$. If the true response probability is $\le 5\%$, there is approximately a 40% probability of terminating patient enrolment during Stage 1. However, if the true response probability is $\ge 20\%$, then there is only a 1.8% probability that a drug will be discarded erroneously in Stage 1.

Page 35 of 53

Protocol: 03/21/16

Up to 28 additional patients (for a total of up to 32) may be treated in order **to gain additional safety and activity information** should the trial be positive at the end of Stage 2. Their safety and efficacy data will be summarized with all other patients at the end of the study.

6.1.1.1. Stage 1

Initially, 18 patients with the indication and treated with AG-013736 will be evaluated for response (CR or PR). Once 1 or more confirmed responses are documented, the study will proceed to Stage 2. If 1 confirmed response has not been documented by the time 18 patients have been started on treatment, enrolment will be temporarily suspended to allow for treatment and evaluation of these patients.

6.1.1.2. Stage 2

In Stage 2, 14 additional patients will be enrolled and treated, to a total sample size of 32 treated patients. If 4 or more responses (CR or PR) are documented among these 32 patients, the indication will be recommended for further study.

6.2. Methods of Analysis

The emphasis of the statistical analyses in this study will be on estimation. Due to the exploratory nature of this study, no imputation of missing data will be done.

An initial assessment will be done after 18 patients with eligible diagnoses have been treated. If there is at least 1 patient with a confirmed response, the trial will be expanded to a total of 32 treated patients with eligible diagnoses. The final analysis will be conducted when at least 1 of the following conditions is met:

- If 4 or more confirmed responses (CR or PR) are documented among the first 32 treated patients enrolled with eligible disease by the end of Stage 2 and the study is not expanded to add additional patients, the final analysis will take place once data have been compiled on all 32 treated patients through at least 1 year from the date of the first dose for the last patient enrolled. The final analysis will occur sooner if the study is discontinued due to lack of clinical response;
- If the study is expanded to derive further information on safety and activity to be used to aid in the design of additional studies with AG-013736 in this indication, then final analysis will take place once data have been compiled on all treated patients through at least 1 year from the date of the first dose for the last patient enrolled.
- The study is complete as defined in Section 3.6.

6.2.1. Primary Efficacy Parameter

The primary efficacy parameter is the overall response rate. All patients who receive at least 1 dose of AG-013736 and have a baseline assessment of disease will be included in the analysis. Patients who were inadvertently enrolled (eg, patients who are determined to have the incorrect histological cancer type after receiving a dose of medication, based on their screening disease

Page 36 of 53

Protocol: 03/21/16

assessment) will be excluded from analyses and will be replaced. The overall response rate is defined to be the percentage of patients with a confirmed CR or PR. Patients who die, progress, or drop out for any reason after receiving a dose of AG-013736 prior to reaching a CR or PR will be included in the analysis as non-responders.

For response rate, duration of response, and progression-free survival, assessments from the independent third party will be considered the primary data. Additionally, the primary analyses for these endpoints will be based on the data collected from the disease assessment method(s) used starting at baseline to follow a patient's lesions. If PET scans or ultrasound is used on some patients during study who are believed to have central tumor necrosis or intratumor bleeding, these data and any subsequently collected lesion assessment data will not be used in the primary analyses but may be used in exploratory analyses of response rate, duration of response and progression-free survival.

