2. STUDY OBJECTIVES

The primary objective of this study is to determine the activity of AG-013736 in metastatic melanoma as measured by the complete response (CR) and partial response (PR) by RECIST. A response will also be considered to have occurred if there is a >/= 25% reduction in the involved nodal basin specific uptake value (SUV) on PET/CT (see Appendix C). Secondary objectives are to:

- Progression free survival
- determine the safety profile of AG-013736
- determine duration of response
- determine overall survival
- obtain blood samples for population pharmacokinetic analyses
- explore relationships between clinical response and plasma soluble proteins
- explore relationships between clinical response with host and tumor genomics

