3. METHODS

3.1. Study Design

This will be a 2-stage Minimax, Phase 2, open-label study of the investigational anti-angiogenesis agent AG-013736 in patients with locally metastatic stage III melanoma.

Patients will be consented at the time of diagnosis of stage III disease based on clinical or biopsy results. After obtaining a baseline PET/CT, patients will undergo 2 months of therapy with axitinib. Response will be determined by restaging PET/CT after two months of initial therapy. (Mohr P, Eggermont AM, Hauschild A, Buzaid A. Staging of cutaneous melanoma. Ann Oncol. 2009 20 Suppl 6:vi14-21.; Kumar R, Mavi A, Bural G, Alavi A. Fluorodeoxyglucose-PET in the

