6.2.2.1.2. Progression-free survival (PFS)

All patients who receive at least 1 dose of AG-013736 and have a baseline assessment of disease will be included in the analysis. Patients who were inadvertently enrolled (eg, patients who are

determined to have the incorrect histological cancer type after receiving a dose of medication, based on their screening disease assessment) will be excluded from analyses.

PFS is defined as the difference in days between the first date that criteria for progression were met or the patient died and the date of first dose of AG-013736. Since the day of first dose and the day criteria for progression were met (or the patient died) are each counted as a full day, 1 day will be added to each calculation. Patients lacking an evaluation of tumor response after their first dose will have their event time censored at 1 day. Patients not experiencing disease progression during the treatment and follow-up periods and who do not die during the treatment period will have their event time censored on the last study date that objective tumor assessments verified lack of disease progression.

An estimate of the PFS curve from the Kaplan-Meier¹² method will be presented. Median event time and a 2-sided 95% confidence interval for the median will be provided.¹³

Duration of Overall Response

Analyses on duration of overall objective response will be done for all patients achieving a PR or CR. Duration of overall objective response is defined as the difference in days between the first date criteria for progression occurred and the first date that criteria for a PR or CR were met. Since the day the criteria for PR or CR were met and the first day criteria for progression occurred are each counted as a full day, 1 day will be added to each calculation. Patients who achieve a PR or CR and who do not experience disease progression during the treatment and follow-up periods and who do not die during the treatment period will have their event time censored on the last study date that objective tumor assessments verified lack of disease progression. Patients who die during the treatment period with no disease progression observed, and still in response, will have their duration calculated using the date of death as a non-censored value. Patients who achieve a PR and then a CR will have times calculated using the date of the PR as the first day.

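### Section 6.2.1 excludes PET data and later lesion data when tumor necrosis or bleeding is suspected, which conflicts with its own baseline-method rule and with a trial whose only scheduled tumor scan is PET/CT

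*Combined protocol and SAP*

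**What the plan says.** Two adjacent sentences in Section 6.2.1 govern which tumor data count. The first bases the primary analyses of response rate, duration of response and PFS on "data collected from the disease assessment method(s) used starting at baseline to follow a patient's lesions". The second sets a condition: "PET scans or ultrasound is used on some patients during study who are believed to have central tumor necrosis or intratumor bleeding". Where it is met, the consequence is that "these data and any subsequently collected lesion assessment data will not be used in the primary analyses". Only exploratory use is left open, for the same three endpoints.

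Elsewhere PET/CT is the routine method for every patient:

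- Section 3.1: "After obtaining a baseline PET/CT, patients will undergo 2 months of therapy with axitinib". On the outcome scan, the same section says: "Response will be determined by restaging PET/CT after two months of initial therapy". After surgery, PET/CT is repeated every 4 months.
- The tumor-measurement row of the Schedule of Tests and Procedures, and its note, name PET/CT, read with RECIST. No other tumor scan is scheduled.
- Section 2, and the synopsis objectives and endpoints, make the SUV part of the primary endpoint: "A response will also be considered to have occurred if there is a >/= 25% reduction in the involved nodal basin", measured as SUV on PET/CT.
- Section 3.5.8 rules out a confirmatory scan before the nodal basin is resected.

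For PFS, Section 6.2.2.1.2 adds: "Patients lacking an evaluation of tumor response after their first dose will have their event time censored at 1 day".

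**The concern.** The exclusion is worded as if PET were an occasional extra. Here it is the scheduled method from baseline on, so the two sentences can give opposite instructions for the same scan. One pre-operative scan decides response, and the involved nodes are then removed. If that scan is set aside, it cannot be repeated.

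The trigger is a belief about the tumor, with no stated criteria, that may arise on treatment and be known together with the scan result. Two analysts could code the same patient differently. The response count feeds both decision rules in Section 6.1.1 (at least 1 of 18 to continue, at least 4 of 32 to recommend further study), so a few such patients could matter.

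**Working it through.** **What an affected patient loses on the literal reading**

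| Suspicion arises | Response | Later lesion data | PFS |
|---|---|---|---|
| At the two-month scan | SUV route lost; whether CT diameters from the same scan are kept is not stated | All excluded from the primary analyses | Censored at day 1, or at the last retained assessment if the CT part is kept; death remains an event |
| Only after surgery | Already recorded, kept | Excluded from that point | Censored at the last retained assessment; death remains an event |

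The patient was dosed and has a baseline assessment, so under Section 6.2.1 the patient stays in the denominator. Section 6.2 imputes nothing. The non-responder rule names death, progression and dropout only. A patient whose data were excluded would probably be counted as a non-responder, but no rule says so.

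**Reproducing the plan's design**

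Inputs from Section 6.1.1: p0 = 0.05, p1 = 0.20, α = β = 0.10, 18 + 14 = 32 patients, continue with at least 1 response in 18, recommend with at least 4 in 32.

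The stage 1 rule stops only at zero responses, so

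P(positive | p) = P(X₃₂ ≥ 4) − P(X₁₈ = 0) × P(X₁₄ ≥ 4), with all X binomial at rate p.

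- p = 0.05: 0.0738 − 0.3972 × 0.0042 = 0.072. This is below 0.10. The early-stopping probability is 0.95¹⁸ = 0.397 (plan: about 40%).
- p = 0.20: 0.9069 − 0.0180 × 0.3018 = 0.901. This meets the planned 0.90. The early-stopping probability is 0.80¹⁸ = 0.018 (plan: 1.8%).

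An exhaustive minimax search returns the same 18/32 design, so the plan's figures reproduce.

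**Effect of losing responders**

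Assume that each true responder is lost with probability q and counted as a non-responder. The counted response rate is then 0.20 × (1 − q). The result is the same if patients are affected regardless of response, because a non-responder whose data are dropped is still a non-responder.

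| q (assumed) | Counted rate | Calculation | Power |
|---|---|---|---|
| 0 | 0.20 | 0.9069 − 0.0180 × 0.3018 | 0.901 |
| 5% | 0.19 | 0.8823 − 0.0225 × 0.2679 | 0.876 |
| 10% | 0.18 | 0.8527 − 0.0281 × 0.2351 | 0.846 |
| 25% | 0.15 | 0.7279 − 0.0536 × 0.1465 | 0.720 |

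The error runs one way. With the same q at a true rate of 0.05, the false-positive probability falls from 0.072 to 0.062, 0.053 and 0.030.

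**The case against.** The strongest reply is that the second sentence merely applies the first. It is conditional and speaks of PET used in some patients during the study, whereas scheduled PET/CT is used in all patients from baseline. On that reading only a mid-study change of method is exploratory, no scheduled scan is lost and the sentences agree. This is plausible as intent. It does not settle the matter, because the text does not say it, no patient is scheduled for a different baseline scan, and the exclusion of later lesion data is not limited by method.

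A second reply is that response can also be reached by RECIST. Appendix C makes RECIST the primary method in addition to PET, and it accepts CT, MRI and clinical examination. The exclusion names PET and ultrasound, not CT, so diameters from the CT part of the two-month scan might survive. This stands as an open question: the text does not say, and none of the other methods is scheduled as a separate response scan. The SUV route would be lost in any case.

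A reader might go further and infer that affected patients have no route to response, are non-responders by rule and lose all PFS information. The documents do not support that. The CT question is open, no rule classifies these patients, deaths still count for PFS, and suspicion that arises only after surgery leaves the response intact. Nor do they show that the exclusion picks out tumors the drug has affected. The Introduction says that reducing tumor vessels may starve a tumor, but it does not link necrosis to response or give its frequency.

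**Conclusion.** The conflict is real. Section 6.2.1 as worded can exclude the scheduled scan that decides response, while the sentence before it and the rest of the protocol require that scan. On the literal reading, a patient suspected of necrosis or bleeding at the two-month scan loses at least the SUV route and all later lesion assessments. If suspicion comes only after surgery, the loss is confined to later PFS and duration data.

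The size is conditional. If 5% to 25% of true responders were lost, power at a 20% rate would be 0.876 to 0.720 against a planned 0.90. This assumes the literal reading, no response credited from the CT part of the scan, and classification as non-responder. The shares are assumptions with no anchor in the documents. On the narrower reading nothing is lost and power stays at 0.901. The finding is therefore a rule on the primary endpoint that must be reconciled, not a demonstrated loss of power.

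**What to change.** Replace the exclusion sentence in Section 6.2.1 with one along these lines: *Scheduled PET/CT data, both SUV and CT measurements, are a baseline assessment method and always enter the primary analyses of response rate, duration of response and PFS, including in patients with suspected tumor necrosis or bleeding; only ultrasound, or unscheduled scans by a method not used at that patient's baseline, are exploratory, and their use does not exclude later scheduled assessments.*

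This settles the status of the CT diameters, and suspected necrosis or bleeding no longer leaves a patient with discarded scans to classify. Carry the same wording into the separate Analysis Plan. Section 6 requires a protocol amendment for major changes to the primary endpoint or its analysis, so record it there.

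The cost is one sentence and its amendment, with no new scans, patients or data.
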